5.6 Safety Analyses

5.6.1 Extent of Exposure

First and last dosing dates will be derived, separately, for each of study drugs (i.e. PEGHPH20 and Eribulin) and overall:

Study Drug	First Dosing date	Last Dosing date
Eribulin	first non-missing eribulin dosing date	last non-missing eribulin dosing date
PEGPH20	first non-missing PEGPH20	last non-missing PEGPH20 dosing date
Overall	Minimum of 2 study drugs' first dosing dates	Maximum of 2 study drugs' last dosing dates

In the analyses, the number of cycles/weeks/doses on treatment, cycle length, cumulative dose received, average dose intensity, relative dose intensity, and the number of subjects with dose reduction/missing, will be summarized by study drug. The data will be listed as well.

Per protocol, one cycle would be 21 days of treatment. The following calculations will be carried out in the analyses:

- The duration of treatment (weeks) for each study drug will be calculated as:
 - (First dosing date of the study drug in the final cycle first dosing date of the study drug in the first cycle + 21)/7.
- The duration of overall treatment (weeks) will be calculated as:
 - (First dosing date of any study drugs in the final cycle First dosing date of any study drugs in the first cycle + 21)/7 (note: '+21' if the first PEGPH20 dose in final cycle was not missing, and '+20' if the first PEGPH20 dose in final cycle was missing and first eribulin dose in the final cycle was not missing).
- The average cycle length of each study drug: will be calculated as the duration of each drug treatment divided by its corresponding number of cycles received in the study.

- Cumulative dose per subject (mg for eribulin, μg for PEGPH20), average dose intensity per subject (mg/m²/week for eribulin and μg/kg/week for PEGPH20), and relative dose intensity per subject (percentage of cumulative dose relative to planned dose):
 - Average dose intensity $(mg/m^2/week)$ for eribulin = total dose (mg)/ baseline $BSA(m^2)/duration$ of eribulin treatment (weeks)
 - Average dose intensity (µg/ kg/week) for PEGPH20= total dose (µg)/baseline weight(kg)/duration of PEGPH20 treatment (weeks)
 - Relative dose intensity (%)=average dose intensity (mg/m2/week for eribulin, µg/kg/week for PEGPH20)/planned dose intensity, where the planned eribulin dose intensity is 0.933 mg/m2/week and the planned PEGPH20 dose intensity is 2 ug/kg/week for dosing level 1 (3 ug/kg) and 1.067 ug/kg/week for dosing level 0 (1.6 ug/kg)

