
Duration of Treatment
 
Those subjects who will be treated with eribulin mesylate and PEGPH20 can remain on eribulin mesylate only or both study drugs in the presence of clinical benefit until unacceptable toxicity or disease progression occurs, or until the subject withdraws consent. Subjects who experience any TE event requiring full dose anti-coagulation while on PEGPH20 treatment will be discontinued from PEGPH20 treatment but may continue to receive eribulin mesylate and remain on the study.
	
Duration of Treatment
 
Those subjects who will be treated with eribulin mesylate and PEGPH20 can remain on eribulin mesylate only or both study drugs in the presence of clinical benefit until unacceptable toxicity or disease progression occurs, or until the subject withdraws consent. Discontinuing either eribulin or PEGPH20 only will be considered as study treatment discontinuation. Subjects who experience any TE event requiring full dose anti-coagulation while on PEGPH20 treatment will be discontinued from PEGPH20 treatment but may continue to receive eribulin mesylate and remain on the study.

Reason(s) for the Amendment:

Added language to clarify the end of treatment definition.

ORIGINAL TEXT	AMENDED TEXT
Section 9.4.4	Section 9.4.4
	
Added text:
 
The RP2D will be selected as a dose which does not exceed 1 DLT per 6 patients or 3 DLTs per 18 patients (during the DLT assessment period) and will also include assessment of the entirety of safety data including dose reductions or discontinuations that occur for either study drug during or after the DLT period.

Reason(s) for the Amendment:

To further clarify rationale behind RP2D selection.

Clinical Study Protocol Amendment

ORIGINAL TEXT	AMENDED TEXT
Section 9.4.7.1	Section 9.4.7.1
Dexamethasone may be used to attenuate musculoskeletal symptoms that may occur in subjects treated with PEGPH20.	Dexamethasone may be used is being given as part of the study dosing regimen in order to attenuate musculoskeletal symptoms that may occur in subjects treated with PEGPH20.
Reason(s) for the Amendment:	
To further clarify that Dexamethasone is a mandated concomitant medication in this study.	

ORIGINAL TEXT	AMENDED TEXT
Section 9.4.7.3	Section 9.4.7.3

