3.2 Overall Study Design and Plan

This was a randomized, open-label, multicenter, Phase 1b/2 study of eribulin mesylate in combination with PEGPH20 versus eribulin mesylate alone in subjects with HER2-negative, HA-high, MBC previously treated with up to two lines of systemic anti-cancer therapy (cytotoxic drugs or targeted anti-cancer agents) in the metastatic setting. CDK4/6 inhibitors and mTOR inhibitors would not be considered as prior lines of therapy. Any single agents or combination of scheduled pre-planned treatments (given concomitantly, sequentially, or both) would be considered as one regimen. Hormonal therapy and bone metastases treatment (eg, bisphosphonates, denosumab, etc) would not be considered forms of systemic anti-cancer therapy.

3.2.1 Phase 1b and Phase 2

Study Phase 1b would occur in two parts (Part 1 and Part 2 ("Expansion Part")):

Part 1: would conduct run-in safety cohorts (dose levels 1, 0, and -1, as necessary) of 6 subjects each, until RP2D to be determined as followed:

- The part 1 would have dose-limiting toxicity (DLT) assessed in the first cycle, and would include at least 1 initial safety run-in cohort in which the first 6 enrolled subjects (with any hyaluronan [HA] level) would receive PEGPH20 at a dose of 3 µg/kg intravenously (IV) on Days -1 and 7 of a 21-day cycle, each dose followed approximately 24 (±4) hours later with eribulin mesylate 1.4 mg/m2 IV on Days 1 and 8 (dose level 1).
- Dose level 1 could be selected as the RP2D if no more than 1 subject had a DLT; otherwise, a second cohort of 6 subjects would receive a lower dose of PEGPH20 at 1.6 μg/kg on Days -1 and 7, each dose followed approximately 24 (±4) hours later with eribulin mesylate 1.4 mg/m2 IV on Days 1 and 8 (dose level 0).
- Dose level 0 could be selected as the RP2D if no more than 1 subject of this second cohort had a DLT; otherwise, a third cohort of 6 subjects would receive PEGPH20 1.6 μ g/kg on Days -1 and 7, each dose followed approximately 24 (±4) hours later with eribulin mesylate at a lowered dose of 1.1 mg/m2 IV on Days 1 and 8 (dose level 1).
- If no more than 1 of 6 subjects in this third cohort had a DLT, the Phase 2 part would proceed with dose level -1 as the RP2D. Otherwise, alternative doses would be explored prior to the start of Phase 2.

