3.2.2 Study Drugs Administration

On Days -1 and 7 of each 21-day cycle, Phase 1b subjects and Phase 2 (Arm A, only) subjects would receive PEGPH20 via IV injection over 10 minutes, approximately 1 mL/minute (a window of +2 minutes would be allowed, ie, infusion could be 10 to 12 minutes). On the following day, approximately 24 (\pm 4) hours after Day -1 and Day 7 doses of PEGPH20, eribulin mesylate via IV injection over 2 to 5 minutes would be administered. Phase 2 subjects in Arm B would receive eribulin mesylate alone on Day 1 and Day 8 of each 21-day cycle.

For the subjects of Phase 1b and Phase 2 Arm A, dexamethasone 8 mg twice daily would be administered orally in each treatment cycle to alleviate musculoskeletal toxicities. Subjects would take dexamethasone orally within 2 hours prior to the beginning of each PEGPH20 and 8 to 12 hours after the completion of the infusions. The investigator might adjust the dose of dexamethasone based on the clinical presentation of each subject.

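### SAP 5.6.1: if a drug's first dose in the final cycle is omitted but its second is given, that drug's treatment duration is one week too long and its relative dose intensity too low

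*SAP*

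**What the plan says.** SAP 5.6.1 gives each drug's duration in weeks as "First dosing date of the study drug in the final cycle first dosing date of the study drug in the first cycle + 21)/7". The extracted text drops the minus sign between the two dates; I read it as a difference. Dosing dates in that section are dates of doses actually given: the table above the formula uses, for eribulin, the "first non-missing eribulin dosing date".

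The overall duration has the same form, applied to the first dose of either drug, but with a correction. The constant 21 becomes "20' if the first PEGPH20 dose in final cycle was missing and first eribulin dose in the final cycle was not missing". The per-drug formula has no such rule.

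Per-drug duration is the denominator of average dose intensity, and so of relative dose intensity (RDI). It is also the numerator of average cycle length. The same section describes RDI as cumulative dose expressed as a percentage of planned dose.

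**The concern.** Each drug has two doses per cycle, 7 days apart. If the first is omitted and the second given, the first dosing date in that cycle is a week later than scheduled. When this happens in the final cycle, 14 days of the cycle remain after that dose, yet 21 are added.

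The SAP foresees omitted first doses. The 20-day rule for overall duration exists only because its anchor moves by one day when PEGPH20 Day -1 is missing and eribulin Day 1 becomes the first dose. The one-day shift in overall duration is corrected and the seven-day shift in per-drug duration is not.

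Two internal conflicts follow. One drug can appear to have been given for longer than treatment as a whole, and RDI no longer matches the SAP's own description of it. The statistics at stake are treatment duration, average and relative dose intensity, and average cycle length, by dosing level and in the subject listings.

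**Working it through.** **Inputs.** Cycle length: "Per protocol, one cycle would be 21 days of treatment" (SAP 5.6.1). PEGPH20 is given "On Days -1 and 7 of each 21-day cycle" (SAP 3.2.2). Eribulin follows "approximately 24 (±4) hours later with eribulin mesylate 1.4 mg/m2 IV on Days 1 and 8" (SAP 3.2.1). Counting days from PEGPH20 Day -1, with no Day 0, PEGPH20 falls at 0 and 7, and eribulin at 1 and 8. The number of cycles k is an assumption for illustration. All other doses are taken as given in full and on time.

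**The SAP's planned intensities reproduce.** Two doses per 3 weeks:
- eribulin: 2 × 1.4 / 3 = 0.933 mg/m²/week
- PEGPH20 level 1: 2 × 3 / 3 = 2 µg/kg/week
- PEGPH20 level 0: 2 × 1.6 / 3 = 1.067 µg/kg/week

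All three match SAP 5.6.1. With no omission, both per-drug durations and the overall duration equal 3k weeks and RDI is 100%. The fault therefore lies in the duration rule for omitted doses, not in the planned rates.

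**Final-cycle PEGPH20 Day -1 omitted; eribulin Day 1 and PEGPH20 Day 7 given; k ≥ 2.**
- PEGPH20 duration = (21(k−1) + 7 − 0 + 21)/7 = 3k + 1 weeks
- Overall duration = (21(k−1) + 1 − 0 + 20)/7 = 3k weeks
- PEGPH20 exceeds overall by exactly 1 week.

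RDI by the SAP formula at level 1 is (2k−1) × 3 / (3k+1) / 2. Doses given over doses planned is (2k−1)/(2k).

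| k | PEGPH20 duration, weeks | Overall, weeks | RDI by SAP formula | Doses given / planned |
|---|---|---|---|---|
| 2 | 7 | 6 | 9/7/2 = 64.3% | 3/4 = 75.0% |
| 4 | 13 | 12 | 21/13/2 = 80.8% | 7/8 = 87.5% |
| 11 | 34 | 33 | 63/34/2 = 92.6% | 21/22 = 95.5% |

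Eleven cycles are 231 days, or 231/30.4375 = 7.6 months, close to the estimated median treatment duration of 8 months in the Protocol synopsis. Average cycle length at k = 2 is 7 × 7 / 2 = 24.5 days instead of 21. Eribulin behaves the same way if its final-cycle Day 1 is omitted and Day 8 given: 3k + 1 weeks against 3k overall.

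**Cycle-1 eribulin Day 1 omitted, Day 8 given.** At k = 2 the duration is (22 − 8 + 21)/7 = 5 weeks rather than 6, and RDI is 3 × 1.4 / 5 / 0.933 = 90.0% against 75.0%. At k = 4 the duration is 11 weeks and RDI is 95.5% against 87.5%.

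**Cases with no RDI error.**
- A first dose omitted in a middle cycle, or any second dose omitted: the two anchor dates do not move.
- A single cycle: first and final dates coincide, and RDI is correct at 50%. For PEGPH20 Day -1 omitted, PEGPH20 duration is 21/7 = 3.0 weeks against 20/7 = 2.86 overall, a one-day excess.

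**Both first doses omitted in the final cycle.** The note on overall duration covers neither constant here. With 21, overall duration is also 3k + 1 weeks; with 20, it is one day less than PEGPH20 duration.

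**The case against.** The arithmetic is hard to dispute, so the best defence concerns scope and consequence.

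- **Omission or delay.** If a withheld first dose moves the whole cycle later, 21 days from the dose given is right. This stands: the point is confined to omitted doses.
- **Cycle 1 as convention.** Starting a drug's duration at its first actual administration is a legitimate definition. This stands in part: the 90.0% is wrong only against the SAP's description of RDI as cumulative over planned dose.
- **A later document may settle it.** SAP 9 leaves derivation rules to a separate dataset specification. That document cannot be assumed to override a formula stated explicitly in the SAP.
- **Small effect.** With one affected subject among the 18 planned at the recommended Phase 2 dose, mean RDI moves by about 2.8/18 = 0.16 points at 11 cycles, or 10.7/18 = 0.6 points at 2 cycles. This stands for means in the larger group. In a run-in cohort of 6, the 2-cycle error moves the mean by 10.7/6 = 1.8 points. One subject can also set the reported minimum or maximum.

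A reader might go further and infer that the error biases the choice of the recommended Phase 2 dose. The documents do not support that. The rule counts dose-limiting toxicities, and the text added to Protocol 9.4.4 calls for "assessment of the entirety of safety data including dose reductions or discontinuations", without naming dose intensity. Numbers of doses, cumulative dose, and counts of subjects with reduced or missing doses do not use the duration formula.

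Nor can one infer that the errors never cancel. Opposite signs can offset across subjects. A subject who misses eribulin Day 1 in both the first and final of two or more cycles gets the correct duration. A claim that the error concentrates in poorly tolerating subjects has no source in the documents, and RDI is correct for those with only one cycle.

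**Conclusion.** The concern holds within stated limits. As written, SAP 5.6.1 overstates a drug's duration by one week when three conditions hold: the subject has at least two cycles, the drug's first dose in the final cycle is omitted rather than delayed, and its second dose in that cycle is given. RDI is then understated by 10.7 points at 2 cycles, 6.7 at 4 and 2.8 at 11, assuming all other doses are full and on time. An omitted eribulin Day 1 in cycle 1 shortens the duration by a week and raises RDI, subject to the convention noted above.

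The documents do not say how often such cycles occur. No hypothesis test or comparison depends on these figures. A broader reading, that any omitted first dose adds a week, is not supported. The reason to act is that a stated rule gives an impossible result in a situation the SAP itself foresees, and that correcting it is nearly free.

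**What to change.** Compute each drug's duration from the cycle rather than from the first dose given: (scheduled first-dose day of the drug in its final cycle − scheduled first-dose day in its first cycle + 21)/7. Define the cycle start, in order of preference, as:

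1. the actual PEGPH20 Day -1 date;
2. otherwise, the eribulin Day 1 date minus 1 day;
3. if both were omitted, the PEGPH20 Day 7 date minus 7 days or the eribulin Day 8 date minus 8 days, or the recorded cycle visit date. The visit date is the safer choice if the second dose was not on time.

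Apply the same anchor to overall duration. This replaces the 20/21 switch and also covers the case where both first doses are missing. In the examples above, per-drug and overall durations all become 3k weeks and RDI equals doses given over doses planned. If the sponsor prefers to start a drug's duration at its first actual administration, the SAP should say so and reword its description of RDI to match.

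Cost: one SAP sentence and one derivation line. No new data are needed, and results do not change for on-schedule subjects without such omissions.

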5.6.2 Adverse Events

The AE verbatim descriptions (investigator terms from the CRF) will be classified into standardized medical terminology using the Medical Dictionary for Regulatory Activities (MedDRA). Adverse events will be coded to the MedDRA (Version 19.1 or higher) lower level term (LLT) closest to the verbatim term. The linked MedDRA preferred term (PT) and primary system organ class (SOC) will also be captured in the database. The CTCAE grading (Version 4.03 or higher) will be considered in the database.

A treatment-emergent adverse event (TEAE) is defined as an AE that emerged during treatment (i.e., AE onset or worsening is on or after first dose date of any study drugs, or up to 28 days following last dose of any study drugs), having been absent at pretreatment (Baseline) or

- Reemerged during treatment, having been present at pretreatment (Baseline) but stopped before treatment, or
- Worsened in severity during treatment relative to the pretreatment state, when the AE was continuous.

Only those AEs that are treatment emergent will be summarized in tables. A subject will be counted only once within each category (ie, SOC, PT, grade, or other specific category to be summarized in table) even if the subject experienced more than 1 TEAE within the category. All AEs, treatment emergent or otherwise, will be presented in subject data listings.

The following TEAE summary analyses will be performed:

• An overview summary table will include number (percentage) of subjects with any TEAE, with any treatment-related TEAE, with any TEAE of grade 3 or above, with any TEAE of grade 3 or grade 4, with any serious TEAE, with any TEAE leading to study drug withdrawal, with any TEAE leading to study drug dose reduction, with any TEAE

leading to study drug interruption, and with any TEAE of special interest. This overall summary will be repeated similarly for treatment-related TEAEs.

- TEAEs will be summarized by SOC, PT and grade in number (percentage) of subjects. Repeat this analysis for the TEAEs that are treatment-related, serious, serious and treatment-related, leading to death/dose modification/dose discontinuation, separately.
- TEAEs will be summarized by PT and grade in number (percentage) of subjects.
- Fatal TEAEs will be summarized by SOC and PT in number (percentage) of subjects. Repeat this analysis for non-fatal TEAEs, for TEAEs leading to study dose withdrawn, and for TEAEs leading to study dose reduction/interruption, separately.
- TEAEs of special interest will also be summarized in number (percentage) of subjects for each type of special interest by PT and grade. Repeat this analysis for treatment-related TEAEs, for serious TEAEs, and for treatment-related and serious TEAEs, separately.

5.6.2.1 Death

All deaths, deaths within 28 days of last dose, and deaths >28 days of last dose will be summarized. Deaths will be listed as well.

5.6.3 Laboratory Values

Clinical laboratory test parameters, per category, are listed in Table 1. The test results will be standardized using System International (SI) units and categorized according to CTCAE grade (v4.03 or higher) (see protocol Appendix 6).

Each laboratory test parameter will be summarized by visit, on the actual value observed, and on its change from baseline (except the parameters from Urinalysis). Grade shifting table from baseline to the worst during treatment period will also be summarized per parameter. The data will be listed as well.

Category	Parameters
Hematology	Hematocrit, hemoglobin, platelets, RBC count, and WBC count with differential (bands, basophils, eosinophils, lymphocytes, monocytes, neutrophils), ANC, Coagulation ^a (PT, PTT, INR)
Clinical Chemistry	
Electrolytes	Sodium, potassium, chloride, calcium, magnesium
Liver Function Tests	ALT, AST, alkaline phosphatase, total bilirubin, direct bilirubin
Renal Function	BUN, serum creatinine
Pregnancy	Serum or urine β-hCG
Other	Albumin, glucose ^b , LDH, total protein, uric acid
Urinalysis (urine dipstick)	Glucose, ketones, pH, protein, blood RBCs, leukocytes, specific gravity. Urine microscopy (if clinically indicated), culture, and sensitivity in case of UTI

Table 1Clinical Laboratory Tests

ALT = alanine aminotransferase, ANC = absolute neutrophil count, AST = aspartate aminotransferase, β -hCG = beta-human chorionic gonadotropin, BUN = blood urea nitrogen, LDH = lactate dehydrogenase, PT=prothrombin time, PTT=partial thromboplastin time, INR=international normalized ratio, RBC = red blood cells, UTI=urinary tract infection, WBC = white blood cells.

a: Coagulation tests at screening visit and when clinically indicated

b: Fasting glucose at screening only

5.6.4 Vital Signs

Each parameter of vital signs assessments (diastolic and systolic BP, pulse rate, respiratory rate, temperature, weight, body surface area) will be summarized by visit on actual value observed and on its change from baseline. The data will be listed as well.

5.6.5 Electrocardiograms

Each parameter of electrocardiogram (ECG) assessments (heart rate, QT interval, QTcB interval, QTcF interval, RR interval) will be summarized by visit on actual value observed and on its change from baseline (or from the first assessment observed during study if no baseline available). The data will be listed as well.

ECG findings (normal, abnormal-not clinically significant, abnormal-clinically significant) will also be summarized on shifting from baseline to the worst during treatment period. The data will be listed as well.

5.6.6 Other Safety Analyses

5.6.6.1 Dose-limiting Toxicity in Phase1b Study

Per protocol, Part 1 Phase 1b subjects would get dose-limiting toxicity (DLT) assessed in the first treatment cycle to determine the RP2D during the study. The DLTs will be summarized and the data will be listed as well.

Per the protocol, the definition of DLT would be one of the following toxicities occurring during the DLT assessment window and considered by the investigator to be related to either of the study drugs:

- Hematologic Toxicities:
 - Any Grade 4 thrombocytopenia or neutropenia lasting >7 days
 - Neutropenia Grade 3 or 4 complicated by fever and/or infection (ANC < 1.0 x 109/L, fever \ge 38.5°C).
 - Thrombocytopenia Grade 3 complicated by bleeding and/or requiring platelet or blood
 - transfusion
- Nonhematologic Toxicities:
 - Any Grade DVT, PE or stroke.
 - Any Grade 4 toxicity.
 - Any clinically significant Grade 3 toxicity EXCLUDING:
 - Nausea, vomiting, or diarrhea controlled by medical intervention within 72 hours.
 - Hypersensitivity reactions Grade 3 or 4 including allergy reactions or anaphylaxis symptomatic bronchospasm requiring parenteral medication(s) with or without urticaria; allergy-related edema/angioedema.
 - Discontinuation or delay of more than 2 weeks of either study drug due to treatmentrelated AE will be considered as a DLT.

5.6.6.2 ECOG Performance Status

ECOG performance status will be summarized on shifting from baseline to the worst during treatment period. The data will be listed as well.

5.7 Other Analyses

No other analysis will be performed.

5.8 Exploratory Analyses

Exploratory analyses may be conducted as appropriate. Any exploratory analyses that are performed will be appropriately titled/labeled as exploratory and will be clearly distinguished from planned analyses when results are reported in the Clinical Study Report.

